13. SUBGROUP ANALYSES

If there is a sufficient number of subjects with presents of one or more anti-SBC-102 antibodies versus those subjects without presence of any anti-SBC-102 antibodies then efficacy analysis will be performed separately for each group.

Post-hoc subgroup analyses may be performed as needed.

14. CHANGES FROM PROTOCOL-SPECIFIED ANALYSES

- 1. Liver cholesteryl ester signature (as measured by ¹³C MRS) will not be analyzed.
- 2. Listings will be sorted by cohort then subject, rather than only by subject.
- 3. ADA, seroconversion data will be listed only.
- 4. Tabulations will be presented overall and by cohort, where cohort is defined by the dose of longest duration, i.e., by the subject's every-other-week dose.
- 5. The protocol states that 'For endpoints that are computed as changes from baseline, a comparison between change from Baseline and change from the CL01 Study Baseline will be performed, as appropriate'. This comparison will be a text description, rather than an additional analysis.
- 6. Liver cholesteryl ester signature (as measured by ¹³C MRS) in a subset of subjects receiving treatment at sites with access to this imaging technology. This will not be analyzed.

16. APPENDICES

16.1 Calculation of Multiples of Normal for Liver and Spleen Volume

Multiples of Normal (MN) are derived by determining the expected "normal" weight of a specific organ based on body weight.

- Liver: 2.5% of body weight in kg gives the expected "normal" liver weight in liters;
- Spleen: 0.2% of body weight in kg gives the expected "normal" spleen volume in liters

For example: a 50 kg subject would have an expected "normal" liver volume of 1.25 liters (0.025*50=1.25) and an expected "normal" spleen volume of 0.10 liters (0.002*50=0.1). The patient's observed organ volume is then divided by the expected "normal" volume. Values of MN >1.0 indicate an organ volume which is larger than the expected normal volume.

16.2 Health-Related Quality of Life Questionnaires

16.2.1 The Functional Assessment of Chronic Illness Therapy (FACIT) Fatigue scale

The FACIT-Fatigue instrument consists of 13 items, with each item rated on a 4-point ordinal scale ranging from 0 (Not at all) to 4 (Very Much).

		Not at	A little	Somewhat	Quite a	Very
		all	bit		bit	Much
1	I feel fatigue	0	1	2	3	4
2	I feel weak all over	0	1	2	3	4
3	I feel listless ("washed out")	0	1	2	3	4
4	I feel tired	0	1	2	3	4
5	I have trouble starting things because I am tired	0	1	2	3	4
6	I have trouble finishing things because I am tired	0	1	2	3	4
7	l have energy	0	1	2	3	4
8	I am able to do my usual activities	0	1	2	3	4
9	I need to sleep during the day	0	1	2	3	4
10	I am too tired to eat	0	1	2	3	4
11	I need help doing my usual activities	0	1	2	3	4
12	I am frustrated by being too tired to do	0	1	2	3	4
	things I want to do					
13	l have to limit my social activity because I am tired	0	1	2	3	4

	Reverse Item?		Item Response	Item Score
1	4	-		=
2	4	-		=
3	4	-		=
4	4	-		=
5	4	-		=
6	4	-		=
7	0	+		=
8	0	+		=
9	4	-		=
10	4	-		=
11	4	-		=
12	4	-		=
13	4	-		=

Scoring of FACIT-Fatigue: The total score ranges from 0-52. Higher scores suggest better quality of life for the subject. All items, except Items #7 and #8, are reversed scored.

Total Score: (sum of Item Scores) * 13 and divide by the number of items answered.

Missing Data: The total FACIT-Fatigue Scale can be calculated as long as more than 50% of the items were answered (e.g. a minimum of 7 of 13 items).

16.2.2 The Chronic Liver Disease Questionnaire (CLDQ)

CLDQ is a 29-item instrument to measure quality of life in 6 domains: abdominal symptoms; fatigue; systemic symptoms; activity; emotional function; and worry. Each item is rated on a 7-point ordinal scale ranging from 1 (All of the time) to 7 (none of the time).

Domains of the CLDQ:

Abdominal Symptoms (AB):	Items 1, 5, 17
Fatigue (FA):	Items 2, 4, 8, 11, 13
Systemic Symptoms (SY):	Items 3, 6, 21, 23, 27
Activity (AC):	Items 7, 9, 14
Emotional Function (EM):	Items 10, 12, 15, 16, 19, 20, 24, 26
Worry (WO):	Items 18, 22, 25, 28, 29;

Scoring of CLDQ:

Single domains and overall score range from 1-7. Higher scores implicate a better quality of life.

Single domain = (Sum individual item scores) x (number of scheduled items per domain) and divide by number of items answered.

Total score = (Sum single domains) divide by 6.

Total score can only be calculated if each single domain score is available.

Missing data:

Single domain scores can be calculated as long as more than 50% of the items were answered (e.g. a minimum of 2 of 3 items, 3 of 5 items, 4 of 8 items)

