10. PATIENT HEALTH-RELATED QUALITY OF LIFE (HRQOL) OUTCOMES ANALYSES

Observed scores and changes from the CL01 and CL04 baseline will be summarized for HRQOL measures including the 36-item Short Form Health Survey (SF-36), Functional Assessment of Chronic Illness Therapy (FACIT-Fatigue) scale, and Chronic Liver Disease Questionnaire (CLDQ). All score data will be presented by study visit in data listings.

For SF-36 scores, scores for the 8 subscales (Physical Functioning, Role Physical, Bodily Pain, General Health, Vitality, Social Functioning, Role Emotional and Mental Health) as well as the Physical Component Summary (PCS) and Mental Component Summary (MCS) will be derived and summarized. Both transformed scores (0 – 100 scoring) and norm-based scores will be presented. The FACIT-Fatigue Total Score, Total CLDQ score, and the 6 subscales of the CLDQ (Abdominal Symptoms, Fatigue, Systemic Symptoms, Activity, Emotional Functions and Worry) will also be listed and tabulated. Observed measurements and changes and/or percent changes from baseline to study time points will be summarized overall and by dosing cohort including 95% confidence intervals.

These analyses will be based on the FAS.

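### The CLDQ domain formula in the SAP is a prorated sum, so it contradicts the SAP's own 1-7 score range and gives the six domains unequal weight in the total.

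*SAP*

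**What the plan says.** SAP Section 16.2.2 sets out the CLDQ as follows.

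- Structure: "CLDQ is a 29-item instrument to measure quality of life in 6 domains". The items are assigned to domains by number; Fatigue, for example, is "Items 2, 4, 8, 11, 13".
- Item scale: responses run from 1 to 7, and a higher score means better quality of life.
- Score range: "Single domains and overall score range from 1-7".
- Domain score: "Single domain = (Sum individual item scores) x (number of scheduled items per domain) and divide by number of items answered".
- Total: "Total score = (Sum single domains) divide by 6", available only when all six domain scores are available.
- Missing items: a domain may be scored when more than half of its items are answered, illustrated by "e.g. a minimum of 2 of 3 items, 3 of 5 items, 4 of 8 items".

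SAP Section 10 commits to listing and tabulating the total CLDQ score and "the 6 subscales of the CLDQ". Observed values, changes and/or percent changes from baseline and 95% confidence intervals are to be given overall and by dosing cohort. Protocol Appendix D reproduces the questionnaire but gives no scoring rule, and SAP Section 14 (changes from protocol-specified analyses) says nothing on it.

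**The concern.** Multiplying by the number of scheduled items and dividing by the number answered gives a sum scaled up for missing items. With complete data it is simply the raw sum. A sum of several items that each score at least 1 cannot have a 1-7 range. The stated range requires a mean.

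The same prorated-sum form appears in SAP Section 16.2.1 for FACIT-Fatigue, where a sum is intended. It may have been carried across, though the documents do not say so.

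The CLDQ is the only one of the three HRQOL instruments that the protocol (Section 5.1.6) describes as specific to chronic liver disease. Protocol Section 3.2.2.4 treats positive HRQOL effects as supporting evidence of benefit, and SAP Section 1 allows the planned analyses into study reports, regulatory submissions and manuscripts. If the formula is programmed as written, CLDQ scores, changes and intervals would be reported on a scale that the SAP itself says is not the CLDQ scale.

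**Working it through.** **Inputs (all SAP 16.2.2).** Item scores 1 to 7. Items per domain, counted from the item lists: Abdominal Symptoms 3, Fatigue 5, Systemic Symptoms 5, Activity 3, Emotional Function 8, Worry 5. Sum: 3 + 5 + 5 + 3 + 8 + 5 = 29, with each of items 1 to 29 used once.

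**Does the plan's 1-7 range reproduce?** Let k be the scheduled items, m the answered items and S the sum of answered scores.

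- As written: domain = S × k / m. All answers at 1 give S = m, so the score is k. All answers at 7 give S = 7m, so the score is 7k. The number of missing items cancels out.
- As a mean: domain = S / m, which runs from 1 to 7 for any k and m.

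| Domain | k | As written | Mean of answered | Weight in total as written (k/29) | Weight if averaged (1/6) |
|---|---|---|---|---|---|
| Abdominal Symptoms | 3 | 3-21 | 1-7 | 10.3% | 16.7% |
| Activity | 3 | 3-21 | 1-7 | 10.3% | 16.7% |
| Fatigue | 5 | 5-35 | 1-7 | 17.2% | 16.7% |
| Systemic Symptoms | 5 | 5-35 | 1-7 | 17.2% | 16.7% |
| Worry | 5 | 5-35 | 1-7 | 17.2% | 16.7% |
| Emotional Function | 8 | 8-56 | 1-7 | 27.6% | 16.7% |

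Total as written: 29/6 = 4.83 to (7 × 29)/6 = 203/6 = 33.83. Total from domain means: 6/6 = 1 to 42/6 = 7. The stated range is reproduced only with means. As written, the total exceeds 7 once the mean item score passes 42/29 = 1.45 (complete data), and Emotional Function can never be 7 or below.

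**Check on the sister formula.** For FACIT-Fatigue (13 items, 0 to 4), the prorated sum has a maximum of 13 × 4 × 13/13 = 52, which matches the 0-52 range stated there. The form is right for FACIT-Fatigue and wrong for a 1-7 scale.

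**Effect on reported changes (illustrative shifts, not taken from the documents).**

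- A 0.5-point gain on every item appears as 0.5 × 3 = 1.5, 0.5 × 5 = 2.5 or 0.5 × 8 = 4.0 on the domains, and as 0.5 × 29/6 = 2.42 on the total. With averaging it is 0.5 throughout.
- Suppose every Emotional Function item improves by 1 point and every Abdominal Symptoms and Activity item worsens by 1. Total as written: (8 − 3 − 3)/6 = +0.33. Averaged total: (1 − 1 − 1)/6 = −0.17. The sign reverses.
- Domain means of 5, except Emotional Function at 3. Total as written: (5 × 21 + 3 × 8)/6 = 129/6 = 21.5. Averaged: (5 × 5 + 3)/6 = 28/6 = 4.67.

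**Missing-item rule.** 2/3 = 66.7% and 3/5 = 60% satisfy a requirement of more than half. 4/8 = 50% does not; 5/8 = 62.5% does. Since the total needs all six domains, a subject with exactly four Emotional Function answers either has a total or has none, depending on which half of the rule is applied.

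**The case against.** The contradiction itself is hard to dispute. The stronger argument is that it matters little.

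- HRQOL is an exploratory objective in a study of up to 9 subjects whose primary objective is safety. SAP Section 10 plans descriptive summaries and intervals for the CLDQ, with no responder threshold or decision rule. This stands, and it limits the consequence.
- Within a domain, the score as written is exactly k times the mean. Percent change, direction of change and whether an interval excludes zero are therefore unaffected, and dividing by 3, 5 or 8 recovers the intended value. The domain scores are to be listed, so the total could be rebuilt too. This also stands for the domains. The tabulated total is different: its weights are wrong, and no rescaling of that total corrects them.
- Some low values fall numerically inside 1-7, such as a 3-item domain scored between 3 and 7. That is true of individual values, but no domain and no total has the stated scale.
- A programmer's range check would probably catch the error. Perhaps so, but the programmer would then have to choose between two SAP statements with no documented basis for the choice.
- The 4-of-8 inconsistency is a separate and smaller defect. It matters only when exactly four Emotional Function items are answered.

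**Conclusion.** The concern holds. The SAP's range statement and its domain formula are incompatible, and nothing else in the SAP or protocol resolves them. As written, domain scores and absolute changes are 3, 5 or 8 times those on the stated scale. The total runs from 4.83 to 33.83 where 1 to 7 is stated, and Emotional Function has 27.6% of the weight where equal weighting gives 16.7%.

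That a mean was intended rests on the SAP's own text. The stated range needs domain means, and dividing the sum of domains by 6 returns a 1-7 total only if each domain is itself on 1-7. The formula is the odd one out. The weights and the range of the total follow from the item lists and need no outside assumption; the 0.5-point and 1-point shifts are illustrations only.

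The reach is limited to one exploratory instrument reported descriptively. Even so, it is a wrong derivation rule for a planned output and should be corrected before analysis.

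**What to change.** In SAP Section 16.2.2:

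1. Define the domain score as the sum of answered item scores divided by the number of items answered.
2. Keep the total as the sum of the six domain scores divided by 6, and state that this is their unweighted mean.
3. Make the missing-item rule agree with its example: either change the 8-item minimum to 5 of 8, or change the threshold to at least half.
4. In the program, add a check that every domain and total lies between 1 and 7.

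The cost is a few lines of SAP text and one derivation. No data collection changes. Made before analysis, the correction avoids a post hoc change of scoring.
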